2.4.2. CV Safety (MACE) Co-Primary Hypothesis

The co-primary CV safety objective will assess the estimand of time to first occurrence (in days) of adjudicated MACE from randomization to the end of study in all randomized subjects regardless of what treatment(s) they go on to receive. The primary analysis will test for non-inferiority of treatment with daprodustat relative to rhEPO, expressed by the following statistical hypotheses:

- Null: daprodustat is inferior to rhEPO, with at least a 25% increased relative risk of first MACE (i.e. the hazard ratio is ≥1.25)
- Alternative: daprodustat is non-inferior to rhEPO (i.e. the hazard ratio is <1.25)

The non-inferiority margin is pre-defined as the hazard ratio of 1.25; supported by a review of evidence reported in historical randomized trials of rhEPO in dialysis and non-

200807 | Statistical Analysis Plan Amendment 3 03 Mar 2021 | TMF-11879471 | 2.0

CONFIDENTIAL

dialysis CKD subjects and after consideration of the largest point estimate that, by design, would meet the statistical criterion for non-inferiority.

Statistical significance of non-inferiority will be assessed at the one-sided 2.5% level. A Cox-Proportional Hazards-Regression model, adjusting for treatment and prognostic randomization stratification factors (dialysis type and region), will be used to estimate the hazard-ratio, its two-sided 95% CI and to generate the p-value for the non-inferiority test. Non-inferiority will be achieved if the upper limit of the two-sided 95% CI is below the margin of 1.25.

The co-primary endpoints will be tested first. Non-inferiority needs to be established for both co-primaries to proceed to evaluate MACE for superiority as well as the principal secondary endpoints for superiority. Principal secondary endpoints include prioritized composites for MACE (including thromboembolic events and hospitalizations for HF) and IV iron utilization (defined as the average monthly IV iron dose used to Week 52). Statistical testing of MACE for superiority as well as the principal secondary endpoints will be adjusted for multiplicity (Section 10.11.1).

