7.2.2. Planned CV Safety (MACE) Co-Primary Statistical Analyses

CV	/ Safety (MACE) Co-Primary Statistical Analyses
	dpoint(s)
•	Time to first occurrence of adjudicated MACE
Мо	odel Specification
•	The Cox Proportional Hazards model will adjust for the following baseline categorical values: o Treatment
	 Dialysis type (as randomized, see Section 10.10.2)
	 Region (as randomized, see Section 10.9 & Section 10.10.2)
•	Confidence intervals for the rate per 100 person-years will also be reported. For within-group rates, the two-sided 95% CI will be obtained using an exact Poisson method. For difference in rates between treatments, the two-sided 95% CI will be constructed with a Normal approximation using Wald's method [Liu, 2006].
•	The co-primary analysis will use only adjudicated safety endpoints as determined by the clinical endpoint committee (CEC) within the time period for follow-up of CV endpoints defined in Section 10.6.4.
•	Calculation of time-to-event or censoring is described in further detail in Section 10.6.4.
•	First occurrence of adjudicated MACE for a subject is defined as the first adjudicated event, determined by the event date, that is indicated as all-cause mortality, non-fatal MI or non-fatal stroke with further details in Section 10.6.4.
Мо	odel Checking & Diagnostics
•	Refer to Appendix 12: Model Checking and Diagnostics for Statistical Analyses.
Мо	odel Results Presentation
•	A summary of the number and percentage of subjects having first-occurrence MACE will be provided by treatment group. The number and percentage of the types of events that make up the first occurrence of MACE will also be provided by treatment group.
•	A summary of all MACE including the number and percentage of subjects and number of events (including first and subsequent MACE) by type of event will be provided by treatment group. Subjects experiencing MACE will be further broken down into subjects who experienced

- group. Subjects experiencing MACE will be further broken down into subjects who experienced exactly one MACE, subjects who experienced exactly two MACE, and subjects who experienced more than two MACE. The number and percentage of subjects in each of these categories by event type combinations will be provided by treatment group.
- The hazard ratio, two-sided 95% CI, one-sided p-value for the statistical non-inferiority test,

200807

CV	Safety (MACE) Co-Primary Statistical Analyses

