of the number of events experienced by subjects. A second model will be run that allows the treatment effects to differ depending on the number of events experienced by subjects. A third model will be run that allows the treatment effect associated with the time to 1st MACE or hospitalization for HF to differ from a common treatment effect estimated for time to 2nd, 3rd, 4th, etc. MACE or hospitalization for HF. The common treatment effect associated with the time to 2nd, 3rd, 4th, etc. in the third model would provide support for a treatment effect on time to subsequent MACE or hospitalization for HF.

It is possible for a patient to die in conjunction with experiencing a series of events in a short time frame. Ultimately, the CEC will identify the primary cause of death. For the purposes of

200807

C	andary Cafaty Chatiatical Analyses, Additional CV Cafaty Endnainte
360	condary Safety Statistical Analyses: Additional CV Safety Endpoints
	analysis of time to first and subsequent MACE or hospitalization for HF, only those events
	occurring prior to and including the 'fatal' event will be included. For example, suppose a
	subject has an MI, followed by a stroke, and dies within a short time frame. If the CEC
	attributes the death to the MI, only the MI will be used in the analysis. If the CEC attributes the
	death to the stroke, both the MI and stroke would be used. If the CEC attributes the death to
	some cause other than the MI and stroke, all three events would be used.
•	Analyses will include only those safety endpoints occurring within the time period for follow-up
	of CV endpoints, with the exception of all-cause mortality, which will use the time period for
	vital status (see Section 10.6.4).
•	For those endpoints or components of endpoints intended to go through the adjudication
	process, only the adjudicated results will be used.
Mo	del Checking & Diagnostics
•	Refer to Appendix 12: Model Checking and Diagnostics for Statistical Analyses.
Мо	del Results Presentation
•	The summary displays of time-to-event endpoints will include a summary of the number and
	percentage of subjects having events. Summaries of composite endpoints will include the
	number and percentage of the type of first occurrence by treatment group.
•	A summary of all time-to-event endpoints including the number and percentage of subjects and
	number of events (including first and subsequent events) by type of event will be provided by
	treatment group.

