• •	• Calculated as the latest randomized treatment dose stop date, for subjects who have a non- missing treatment start date. Note that this date could come from a randomized treatment exposure record with a missing or partial dose stop date if the associated dose start date for that exposure record is on or after the last non-missing randomized treatment dose stop date.			
	 '31' will be used for the day and 'Dec' will be used for the month, unless the study completion or withdrawal date also occurs in the same year; in this case, the study completion or withdrawal date will be used. Missing day, month and year: The study completion or withdrawal date will be used only for subjects 			
	who have a non-missing treatment start date.			
End	of Treatment Value			
	 Only defined for subjects with a non-missing treatment start date Hgb, iron, transfusion and PRO parameters: the latest value on or before the treatment stop date + 1 day. Blood pressure, central laboratory, and vital signs parameters: the latest value on or before the last non-zero dose date + 1 day. 			
Stud	ly Completion/Withdrawal Date			
	 Date of withdrawal for subjects withdrawing (i.e., subjects who actively withdraw or are deemed lost to follow-up) from study or date of completion of study for subjects who complete the study. If the date of study withdrawal entered in the eCRF is before the last study contact date, the last study contact date will be used as the study withdrawal date for analysis. 			
	 Note: Subjects who die while on study are considered as having completed the study 			
	 The eCRF allows for the possibility of missing or partial dates to be recorded for the study completion/withdrawal date on the Study Conclusion form (i.e., missing day, or day and month, or day and month and year). In such a case, or in case of subjects who are missing a Study Conclusion form, the following conventions will be applied in order to impute a study completion/withdrawal date: Missing day: 			
	 The last day of the month will be used, unless the last study contact date also occurs in the same month; in the case, the last study contact date will be used. 			

200807

the last study contact date also or last study contact date will be use	Dec' will be used for the month, unless ccurs in the same year; in this case, the ed.
 Missing day, month and year: The last study contact date will be 	
Planned/Actual Visit Dates	
Planned/actual visit dates will be defined as follow	

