	contact with subject visit, CV endpoint (other than death), AE or SAE date, or
	date last known to be alive then impute the missing day of death as equal to this
	date instead. For example:
	 If –FEB2016 is given as the death date and there is a non-fatal MI on
	08FEB2016, then the imputed date of death would be 08FEB2016 rather
	than 01FEB2016 such that the death is not before the non-fatal MI.
	 If –MAR2016 is give as the death date and the latest date is a non-fatal
	MI on 08FEB2016 then the imputed date of death would be 01MAR2016.
0	If the month and day of the month of death are missing, then impute as 01JAN
	(e.g.,2016 would impute as 01JAN2016). However, if this imputed date
	results in a date that is prior to the latest clinic visit, telephone visit, other contact
	with subject visit, CV endpoint (other than death), AE or SAE date, or date last
	known to be alive then impute the missing month and day of death as equal to
	this date instead. For example:
	If2016 is given as the death date and the latest date is a non-fatal MI
	on 08FEB2016 then the imputed date of death would be 08FEB2016
	rather than 01JAN2016 such that the death is not before the non-fatal MI.
	If2017 is given as the death date and the latest date is a non-fatal MI
	on 08FEB2016 then the imputed date of death would be 01JAN2017.
0	For deaths that occur after subjects have prematurely withdrawn from the study,
	missing or partial dates will be imputed as specified above except if the
	imputation places the death prior to or on the premature withdrawal date. In this
	case the death date will be imputed as the premature withdrawal date
Missing or Par	ial Hospitalization End Dates
•	zation end dates are missing or partial, the following rules for missing or partial
	implemented as long as the imputed date is before the next hospitalization start
	dy completion/withdrawal date (if there is no next hospitalization start date). If the
	te is after the next hospitalization start date, then the date of the next
	tion start date – 1day will be used as the hospitalization end date. If the imputed
	r the study completion/withdrawal date, then the date of the study

CV Safety Endpoints
completion/withdrawal date will be used as the hospitalization end date.
 If only the day of the month is missing, impute the last day of the month (e.g., MAR2016 would impute as 31MAR2016)
 If the month and day of the month are missing, impute 31DEC (e.g.,2016 would impute as 31DEC2016)

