 First event incidence rate (per 100 person years) = (100 * number of subjects with at least 1 event) / first event person years
• First event absolute rate difference (per 100 person years) = daprodustat incidence rate (per 100 person years) – rhEPO incidence rate (per 100 person years)
Evaluation Time Periods for CV Endpoints
Time Period for Follow-up of Cardiovascular Endpoints
The period for capturing CV safety endpoints begins at randomization. The end of this time period is the date of study completion/withdrawal, with the exception that if a death has been reported in the clinical database after this time, then the death will be included in the analysis.
Any endpoints that occurred before the start of this time period are considered to be prior to the time period for follow-up of cardiovascular safety events, and any endpoints that occurred after the end of this time period are considered to be post the time period for follow-up of cardiovascular safety endpoints.
Time Period for Vital Status
The period for capturing vital status begins at the date of randomization. The end of this time period is defined as follows:
For all subjects known to have died, use the date of death
• For all subjects who complete the study, use the study completion date (see Section 10.6.1)
• For all subjects who withdraw from the study, but vital status has been ascertained, and are known to have not died – use the latest date last known to be alive. If vital status has not been ascertained following study withdrawal, use the study withdrawal date
Any endpoints that occurred before the start of this time period are considered to be prior to the time period for vital status, and any endpoints that occurred after the end of this time period are considered to be post the time period for vital status.
Time Period for On-treatment Cardiovascular Endpoints
The period for capturing on-treatment CV safety endpoint events begins at the treatment start date The end of this time period is defined as follows:
 For subjects whose last non-zero dose date is missing and who took randomized treatment, use date of study withdrawal/completion
 For subjects continuing on study past the last non-zero dose date +28 days, use (last non-zero dose date + 28)
 For subjects whose study withdrawal/completion date is on or before (last non-zero dose date +28), use date of study withdrawal/completion

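### The co-primary MACE window counts deaths after completion or withdrawal without a date limit but censors withdrawn survivors at withdrawal, so the end of follow-up depends on the outcome

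*SAP*

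**What the plan says.** Section 7.2.2 restricts the co-primary MACE analysis to adjudicated events "within the time period for follow-up of CV endpoints defined in Section 10.6.4". Section 10.6.4.1 then fixes when that period closes: "The end of this time period is the date of study completion/withdrawal". The same sentence goes on to make one carve-out, which reads: "the exception that if a death has been reported in the clinical database after this time, then the death will be included". The paragraph after it classes endpoints later than the end of the period as falling after it.

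Four other rules bear on this.

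- **Vital-status window (Section 10.6.4.1).** For withdrawn subjects whose status was ascertained and who are known not to have died, the instruction is to "use the latest date last known to be alive". Section 8.2.2.2 reserves this window for one endpoint and leaves the others on the CV follow-up window. Its words are "with the exception of all-cause mortality, which will use the time period for", and the window it then names is the vital-status one.
- **Withdrawal date (Section 10.6.1).** If the recorded withdrawal date precedes the last study contact, "the last study contact date will be used as the study withdrawal date for analysis". Contact is defined broadly and includes third parties and medical records.
- **Death dates (Section 10.6.4.1).** Imputation rules are given "For deaths that occur after subjects have prematurely withdrawn from the study", so such deaths are expected in the data.
- **Estimand (Section 2.4.2).** The target is the time to first "adjudicated MACE from randomization to the end of study in all randomized subjects", whatever treatment they receive.

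**The concern.** Take two subjects who withdraw on the same day without a MACE. One dies a year later and the death reaches the database. The other is found alive on that same later date, for example through a public registry. The first contributes a further year at risk and an event. The second contributes nothing after withdrawal. Whether time after withdrawal counts is decided by what happens in it, so censoring is not independent of the outcome.

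Within each arm this raises the incidence rate per 100 person-years, because the person-time that would offset the added deaths is missing. Between arms, the hazard ratio moves when the share of such subjects differs, through unequal withdrawal or unequal finding of deaths. The trial is open-label, so either is plausible. More withdrawal or fuller death capture in the rhEPO arm pushes the hazard ratio down, towards non-inferiority. The opposite imbalance costs power.

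Separately, the exception has no upper date. A death reported after a completer's end-of-study date would count as a co-primary event although the estimand stops at the end of study.

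**Working it through.** **Reference figures from the SAP.** The margin is 1.25, alpha is one-sided 0.025, the minimum is 664 first MACE, and allocation is 1:1. The SAP states no power, event rate or withdrawal rate, so there is no figure of its own to reproduce.

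- SE of log HR = 2/√664 = 0.0776.
- Largest passing HR = exp(ln 1.25 − 1.96 × 0.0776) = exp(0.2231 − 0.1521) = 1.074.
- Power at true HR 1.0 = Φ(0.2231/0.0776 − 1.96) = 82%.

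**Simulation.** It used 600,000 subjects per arm and an unadjusted Cox hazard ratio. Every rate is an assumption:

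- rhEPO MACE rate 12 per 100 person-years, with 65% of the hazard fatal;
- follow-up uniform over 1.5 to 4 years;
- withdrawal independent of risk;
- later deaths counted only up to the end of study, and no later-contact credit for survivors.

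Each cell gives the HR with everyone censored at withdrawal, then the HR under the SAP rule. Arms are daprodustat vs rhEPO.

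| Withdrawal per 100 PY | Deaths captured | True HR 1.0 | True HR 1.25 |
|---|---|---|---|
| 4 vs 4 | 80% vs 80% | 1.004, 1.004 | 1.253, 1.252 |
| 8 vs 8 | 80% vs 80% | 1.004, 1.005 | 1.248, 1.247 |
| 5 vs 3 | 80% vs 80% | 1.000, 1.014 | 1.253, 1.268 |
| 3 vs 5 | 80% vs 80% | 1.002, 0.990 | 1.254, 1.238 |
| 8 vs 4 | 80% vs 80% | 1.002, 1.030 | 1.248, 1.280 |
| 4 vs 8 | 80% vs 80% | 1.000, 0.973 | 1.250, 1.216 |
| 4 vs 4 | 50% vs 90% | 1.004, 0.991 | 1.251, 1.235 |
| 4 vs 4 | 90% vs 50% | 0.996, 1.009 | 1.242, 1.256 |

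The added deaths were about 2.5% to 5.9% of events.

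**Effect on the test at 664 events.** With b = ln(HR under the SAP rule / HR with the common stop), type I error at HR 1.25 = Φ(−1.96 − b/0.0776).

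- 4 vs 8: b = ln(1.216/1.250) = −0.0276, giving 0.054.
- 3 vs 5, or capture 50% vs 90%: b = −0.0128, giving 0.036.
- 8 vs 4: b = ln(1.280/1.248) = 0.0253, giving 0.011. Power at HR 1.0 is Φ((0.2231 − 0.0253)/0.0776 − 1.96) = 72%.

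**Sensitivity to mortality after withdrawal.** A separate simulation at true HR 1.0 assumed a death hazard of 0.08 and a non-fatal MACE hazard of 0.04 per year, with follow-up of 1.5 to 3.5 years. Relative to the common stop, the shift was 1.024 at 6% vs 3% withdrawal per year and 0.979 at 3% vs 6%. With mortality doubled after withdrawal it was 1.042 and 0.958.

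**Sensitivity to the last-contact rule.** A re-run of that set-up assumed that half of the withdrawn survivors with known status have a contact at the end of study. The shift fell from 1.023 to 1.004 (6% vs 3%) and from 0.976 to 0.994 (3% vs 6%). With doubled mortality at 6% vs 3% it fell from 1.042 to 1.026.

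**The case against.** The strongest defence is the last-contact rule in Section 10.6.1. Because contact is defined so broadly, many withdrawn survivors may already have their clock extended, and the shift can fall below 1%. This stands as a reduction in size. It does not remove the asymmetry: a survivor known alive only through another source, such as a public registry, still ends at withdrawal or the last contact.

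Second, the tipping-point analysis in Section 7.2.2 varies outcomes for withdrawn subjects from a zero to an infinite event rate, by arm. It imputes only prematurely censored subjects, so the added deaths remain events in every scenario. The supportive analysis to the 664th MACE adds a calendar cut-off only. No listed MACE analysis stops all components at withdrawal.

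Third, the exception might be read as covering late reporting rather than late death. But a death dated inside the window already counts and would need no exception. The imputation rule for deaths after withdrawal also points the other way.

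Fourth, deaths after withdrawal but before the end of study belong to an estimand in all randomized subjects. That is correct. Only deaths after a subject's end of study conflict with it, and the simulations do not size those.

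Finally, following survivors to the known-alive date, as for all-cause mortality, may look like the obvious primary rule. In the first simulation, at true HR 1.0, it gave 0.988 at 8 vs 4 (common stop 1.002) and 1.014 at 4 vs 8 (common stop 1.000). That is about 1% in the opposite direction, because non-fatal events are not captured after withdrawal. It does not correct unequal death capture either.

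**Conclusion.** The rule makes the end of follow-up for the co-primary endpoint depend on the outcome, and it conflicts with the estimand for deaths after the end of study. Under the assumed rates the hazard ratio is unaffected when withdrawal and death capture are equal. It shifts by roughly 1-3% in either direction when they differ: under 1% at 6% vs 3% withdrawal if half of the survivors have late contacts, and about 4% if mortality doubles after withdrawal. The 4% figure is relative to the common stop, which is itself not the truth when withdrawal marks higher risk.

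A reader might infer that the hazard ratio is biased whenever the arms differ, or that the non-inferiority test is unsound. The SAP does not support either. It gives no withdrawal or capture rates, and opposing differences can cancel. The 1.074 limit is for the minimum event count. Section 7.2.2 says 664 had already been passed and later events are included; at an assumed 800 events the limit is exp(ln 1.25 − 1.96 × 2/√800) = 1.088. Still, a 1-3% shift is not trivial against that room, and its direction is unknown in advance. Severity: should fix.

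**What to change.** In Section 10.6.4.1, use one end date for events and censoring, whatever the outcome.

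- **Co-primary Cox model (preferred).** Stop every MACE component, including death, at study completion or withdrawal as derived in Section 10.6.1. In the first simulation this matched the full-follow-up HR within 0.002, given withdrawal independent of risk.
- **Sensitivity analysis.** Include post-withdrawal deaths up to the end-of-study date, taken as the middle of the end-of-study window for non-completers. Censor withdrawn survivors at the latest date known alive, under the same cap.
- **Minimum.** If the exception is kept, cap deaths at the end of study and report the analysis censored at withdrawal beside the co-primary result.

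The cost is SAP wording, since the SAP already derives the dates needed. The downside is small: some known post-withdrawal deaths leave the primary count. At the simulated 2.5% to 5.9% of events, that is about 17 to 39 of 664 (664 × 0.025 and 664 × 0.059). They remain visible in the sensitivity analysis and in all-cause mortality.
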